7.6.2. Secondary Endpoints

7.6.2.1. Change from Baseline in PR-PCSS Rating at Days 22 and 43

The baseline PR-PCSS ratings and the level of change in PR-PCSS ratings from Baseline (Screening) at Day 22 and 43 will be summarized using frequency counts and percentages for each severity rating and with mean and SD.

In addition, the PR-PCSS ratings at Day 22 and 43 will be compared with Baseline ratings using similar analysis as mentioned for primary endpoint. Refer to Section 7.6.1.1 for more details.

7.6.2.2. Change from Baseline in CR-PCSS Rating at Days 22, 43, and 71

The baseline CR-PCSS ratings and the level of change in CR-PCSS ratings from Baseline (Screening) at Days 22, 43, and 71 will be summarized using frequency counts and percentages for each severity rating and with mean and SD.

In addition, the CR-PCSS ratings at Days 22, 43, and 71 will be compared with Baseline ratings using similar analysis as mentioned for primary endpoint. Refer to Section 7.6.1.1 for more details.

7.6.2.3. Changes in the Hexsel CSS Total Score from Baseline at Days 22, 43, and 71

The baseline Hexsel CSS scores and the level of change in Hexsel CSS scores from Baseline (Screening) at Days 22, 43, and 71 will be summarized using frequency counts and percentages for each severity scores and with mean and SD.

In addition, the Hexsel CSS total score ratings at Days 22, 43, and 71 will be compared with Baseline using similar analysis as mentioned for the primary endpoint. Refer to Section [7.6.1.1](#) for more details.

7.6.3. Tertiary Endpoints

7.6.3.1. Proportion of Subjects with No Change (or Worsening) from Baseline in PR-PCSS Rating on Days 161 and 251

The proportion of subjects with complete loss of response as provided in Section [4.5.5](#) in PR-PCSS rating will be summarized using frequency counts and percentages.

7.6.3.2. Proportion of Subjects with No Change (or Worsening) from Baseline in CR-PCSS Rating on Days 161 and 251

The proportion of subjects with complete loss of response as provided in Section [4.5.5](#) in CR-PCSS rating will be summarized using frequency counts and percentages.

7.6.3.3. Proportion of Subjects with No Change (or Worsening) from Baseline in Hexsel CSS Total Score on Days 161 and 251

The proportion of subjects with complete loss of response as provided in Section [4.5.5](#) in Hexsel CSS total score will be summarized using frequency counts and percentages.

7.7. Safety Analyses

Safety data will be summarized using the Safety Population.

7.7.1. Study Drug Exposure

The following will be summarized at each treatment session by treatment area for each treatment region using descriptive statistics:

- Number of injections given.
- Number of dimples treated.
- Average number of injections per dimple.
- Duration of exposure (refer to [Table 12](#) for computation of exposure duration).
- Total dose administered.

The number of subjects treated at each treatment session will be summarized using frequency counts and percentages by treatment area for each treatment region.

A subject listing of overall exposure and injection status will be provided.

7.7.2. Adverse Events

All AE summary tables will include TEAEs and the AEs before the first injection.

AEs will be summarized by SOC and PT and by treatment region and overall as frequency counts and percentages of subjects with AEs and number of AEs (total events), unless otherwise specified.

A subject will only be counted once per SOC and PT.

For AEs by severity grade (mild, moderate, severe), if a subject has multiple events occurring in the same SOC or same PT, then the event with the maximum intensity (ie, severe) will be counted.

For AEs by relationship to study drug, if a subject has multiple events occurring in the same SOC or same PT, the event with the highest association (ie, related) to study drug will be summarized.

AEs will be presented in decreasing order of the incidences at SOC level and within each SOC, in decreasing order of the incidences at the PT level.

An overall summary of AEs and AEs related to study drug will be presented and will include:

- Any AE.
- Any mild, moderate and severe AE.
- Any study drug related AE.
- Any serious AEs.
- Any study drug related serious AE.
- Any AEs leading to study drug interruption/discontinuation.
- Any study drug related AEs leading to study drug interruption/discontinuation.
- Any AEs leading to study withdrawal.
- Any study drug related AEs leading to study withdrawal.
- Any AEs resulting in death.
- Any study drug related AEs resulting in death.
- Any AESIs.

The following summary tables will be presented by SOC and PT:

- All AEs.
- AEs by Severity.
- TEAEs by Relationship to Study Drug.
- Serious AEs.
- Serious study drug related TEAEs.
- TEAEs leading to study drug interruption/discontinuation.

- Study drug related TEAEs leading to study drug interruption/discontinuation.
- AEs leading to study withdrawal.
- Study drug related TEAEs leading to study withdrawal.
- AEs resulting in death.
- Study drug related TEAEs resulting in death.
- AESIs.

Most common non-serious AEs by order of frequency (most frequent, 2nd most frequent, and 3rd most frequent) will be summarized by PT. Most common non-serious AEs are any PT that at least 5% of the subjects reported at least once.

The following listings will be presented by subject:

- All AEs.
- Serious AEs.
- AEs resulting in drug interruption/discontinuation.
- AEs resulting in study withdrawal.
- AEs resulting in deaths.
- AESIs.

Refer to [Table 12](#) for computation of duration of AEs.

7.7.3. Clinical Laboratory

Laboratory parameters (hematology and chemistry) results will be summarized by treatment region, not treated and overall using descriptive statistics for observed and change from baseline values at Baseline (Screening), Day 71, and Day 251.

PCI laboratory values will be summarized by frequency counts and percentages. Refer to [Table 9](#) for PCI criteria.

Individual laboratory results including hematology, chemistry, urinalysis, blood serology, serum and urine pregnancy test results will be listed.

7.7.4. Vital Signs and Body Weight

Vital signs parameters (blood pressure, pulse rate, respiratory rate, and body temperature) and body weight will be summarized by treatment region, not treated and overall using descriptive statistics for observed and change from baseline values for all visits/time points.

PCI vital sign values will be summarized by frequency counts and percentages. Refer to [Table 10](#) for PCI criteria.

Individual vital sign measurements including pulse rate, systolic blood pressure, diastolic blood pressure, respiratory rate, and body temperature will be listed.

7.7.5. 12-Lead ECG

A subject listing will be presented for the investigator interpretation.

7.7.6. Physical Examination

A subject listing will be presented for the physical examination (by body system) for Screening results.

7.7.7. Immunogenicity

Binding anti-AUX-I and anti-AUX-II antibody data will be summarized using the number of subjects with an immunogenicity sample, the frequency counts and percentages of subjects with a positive sample, and a descriptive summary of the average titer level of the positive samples at Day 1, Day 71, Day 161, and Day 251. The titer levels will be logarithmically transformed prior to being summarized descriptively.

The frequency counts and percentages of assayed serum samples that will detect the presence or absence of neutralizing antibodies (positive/negative) to AUX-I and AUX-II will be summarized by treatment region and overall using frequency counts and percentages at all visits.

Listings of immunogenicity data will be presented for all subjects.

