2.1. Study Rationale

The results from Phase 2 (buttock and thigh) and Phase 3 (buttock) studies show CCH 0.84 mg given per treatment area (1 buttock or 1 thigh) is an effective treatment for edematous fibrosclerotic panniculopathy (EFP, commonly known as cellulite) based on improvement in the severity of cellulite as determined by the Investigator and the subject. There were no safety concerns following 3 doses of 0.84 mg of CCH per treatment area. The majority of adverse events (AEs) occurred at the site of injection and resolved before the next scheduled treatment in these studies. The immunogenicity profile of CCH has been consistent across all studies.

The efficacy of CCH treatment on cellulite has been demonstrated in previous clinical studies using validated photonumeric scales. This study will capture the change from baseline after CCH treatment using the validated photonumeric scales and explore tissue level changes in the treatment areas (buttocks and thigh), both from histopathology and radiology perspectives.

COVID-19 Public Health Emergency Impact

The COVID-19 public health emergency has disrupted the conduct of clinical research throughout the world. At Endo Pharmaceuticals Inc. (Endo) ensuring the safety of clinical study participants is our primary concern. In addition, the integrity of data obtained from clinical trials must be ensured.

Endo initiated study EN3835-212 at a single investigational site in November of 2019. The first subject was dosed with CCH on 26 December 2019. On 18 March 2020, the investigational site suspended Study EN3835-212 due to the COVID-19 public health emergency. At that time, 7 subjects had received at least 1 dose of CCH in this study. Of those 7 subjects, 2 had completed the 3 doses required for the study and 1 subject had completed 2 doses. No subjects had completed all assessments required for the Day 71 Visit or beyond.

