On 15 April 2020, all 7 subjects were more than 1 week outside of the visit window for their next dose or for the Day 71 visit and there was no indication that the site would be able to re-open within the following 2 weeks. In order to ensure subject safety and protect data integrity, Endo, in accordance with the *FDA Guidance on Conduct of Clinical Trials of Medical Products during COVID-19 Public Health Emergency* (March 2020, updated 16 April 2020), decided to add additional subjects and modify the assessments required for current subjects when the investigational site re-opens as follows (and with subject consent):

- Subjects who were in screening for the study at the time of interruption (18 March 2020) but who had not been dosed with CCH will repeat all screening assessments to determine eligibility, if willing to do so. All screening assessments must be repeated within the screening window.

- Subjects who had received less than 3 doses of CCH prior to 18 March 2020 will be allowed to continue in the study and may receive any remaining doses with Sponsor approval. These subjects will complete all remaining visits and assessments EXCEPT biopsies and biopsy follow-up visits, if willing to do so. These subjects will be included in the safety assessments for the study, but will not be included in the efficacy assessments. Subjects who received less than 3 doses prior to 18 March 2020 may elect to remain in the study without receiving additional doses.
- Subjects who received all 3 doses of CCH prior to 18 March 2020, will be allowed to continue in the study and complete all remaining visits and assessments (including biopsies and biopsy follow-up visits), if willing to do so. These subjects will be included in the safety assessments for the study, but will not be included in the efficacy assessments. Subjects who received all 3 doses of CCH prior to 18 March 2020 may elect to remain in the study without completing the biopsies and biopsy follow-up visits.
- An additional 12 subjects will be dosed in the study. These subjects will be included in the safety assessments and all efficacy assessments will be based on the data for these 12 subjects.

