4. STUDY DESIGN

4.1. Overall Design

This is a single-center, open-label, Phase 2a study to assess the safety and efficacy of CCH in adult women with moderate or severe EFP of the buttocks or thighs using photonumeric scales, MRI, and histopathology of tissues from the treated area. Approximately 19 subjects will be dosed in this study.

This study was suspended due to the COVID-19 public health emergency on 18 March 2020. When the study re-opens, subjects who had received less than 3 doses of CCH prior to 18 March 2020 will be allowed to continue in the study and may receive any remaining doses with Sponsor approval. These subjects will complete all remaining visits and assessments EXCEPT biopsies and biopsy follow-up visits, if willing to do so. These subjects will be included in the safety assessments for the study, but will not be included in the efficacy assessments. Subjects who received less than 3 doses prior to 18 March 2020 may elect to remain in the study without receiving additional doses.

Subjects who received all 3 doses of CCH prior to 18 March 2020, will be allowed to continue in the study and complete all remaining visits and assessments (including biopsies and biopsy follow-up visits), if willing to do so. These subjects will be included in the safety assessments for the study, but will not be included in the efficacy assessments. Subjects who received all 3 doses of CCH prior to 18 March 2020 may elect to remain in the study without completing the biopsies and biopsy follow-up visits.

An additional 12 subjects will be dosed in the study. These subjects will be included in the safety assessments, and all efficacy assessments will be based on the data from these 12 subjects. For the 12 subjects who receive their first dose of study drug after 18 March 2020, every attempt will be made to enroll an equal number of subjects across the 2 severity levels in both buttocks and thighs (eg, 3 subjects with moderate buttock cellulite, 3 subjects with severe buttock cellulite, 3 subjects with moderate thigh cellulite, and 3 subjects with severe thigh cellulite).

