8. CHANGE FROM PROTOCOL

This SAP is prepared primarily based on the study protocol; original version dated October 22, 2019 and protocol amendment 1 dated January 16, 2020.

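### Applied to the Amendment 3 Safety Population, the pre-interruption SAP would mix up to 7 COVID-interrupted women, up to 5 of them with 1 or 2 doses or a late-completed course, into its Day 71 and later antibody summaries

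*SAP*

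**What the plan says.** **SAP.** Immunogenicity sits under Safety Analyses (SAP 7.7), which use the Safety Population. SAP 7.7.7 summarises binding antibodies by number sampled, number and percentage positive, and "a descriptive summary of the average titer level of the positive samples at Day 1, Day 71, Day 161, and Day 251". Neutralizing antibodies are given as positive or negative at all visits, by treatment region and overall. On its basis, SAP 8 states: "This SAP is prepared primarily based on the study protocol; original version dated October 22, 2019 and protocol amendment 1 dated January 16, 2020". SAP 9 calls it the first version, and SAP 3.1 and 3.3 still plan about 12 dosed subjects. The SAP's Safety Population (Table 11) has no cut at 18 March 2020.

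**Protocol, Amendment 3.** Section 2.1 reports that 7 women had been dosed when the site suspended the study on 18 March 2020: "Of those 7 subjects, 2 had completed the 3 doses required for the study and 1 subject had completed 2 doses". It adds "No subjects had completed all assessments required for the Day 71 Visit or beyond". Of the position on 15 April 2020 it says: "all 7 subjects were more than 1 week outside of the visit window for their next dose or for the Day 71 visit". Under Section 4.1, women with fewer than three doses "will be allowed to continue in the study and may receive any remaining doses with Sponsor approval", or "may elect to remain in the study without receiving additional doses"; in either case they complete the remaining visits, apart from biopsies and biopsy follow-up, if willing. All 7 count for safety and none for efficacy. Twelve further women are to be dosed, about 19 in all. Section 9.3.4 also summarises antibodies at Days 1, 71, 161 and 251 without a split.

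**The concern.** Change in binding and neutralizing antibodies is a named secondary safety endpoint (Protocol 3), and Day 71 is the first antibody sample after dosing. In the planned regimen that sample comes about four weeks after the third dose. For an interrupted woman, a sample with the same label can follow one, two or three doses, at an interval that was never planned.

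Antibody response can plausibly depend on the number of doses and the time since the last one. This is general reasoning; the documents give no figure for it. If it is so, a pooled percentage positive or mean titre at Day 71 would not describe the three-dose course, yet a reader of the table would probably take it that way.

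The protocol already treats these women as not comparable elsewhere. It leaves them out of efficacy and replaces them all, and at the interim it assesses the MRI and biopsy data of the three-dose women separately (Protocol 9.4). The by-visit antibody summaries have no matching provision.

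**Working it through.** **Counts** (Protocol 2.1 and 4.1)
- Reproducing the plan's total: 7 + 12 = 19, as stated.
- Doses at suspension: 2 women with three, 1 with two, so 7 − 2 − 1 = 4 with one. Fewer than three: 4 + 1 = 5.
- Shares of dosed women: 7/19 = 36.8% interrupted; 5/19 = 26.3% with fewer than three doses; 2/19 = 10.5% with all three. These are maxima, because continued attendance is voluntary.

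**Exposure at Day 71** (Protocol Table 2, maximum doses)
- Planned: 3 × 1.68 = 5.04 mg. One dose only: 1.68/5.04 = 33%. Two doses only: 3.36/5.04 = 67%.
- If none of the 5 resumes and all 19 are sampled, mean doses in the column are (4×1 + 1×2 + 14×3)/19 = 48/19 = 2.53 instead of 3. The titre average covers positive samples only, so 2.53 is not the exposure behind that average.

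**Planned timing** (visit windows ±3 days at Days 22 and 43, +10 days at Day 71)
- Dose 1 to dose 2: 21 days, range 19 − 1 = 18 to 25 − 1 = 24.
- Dose 2 to dose 3: 21 days, range 40 − 25 = 15 to 46 − 19 = 27.
- Dose 3 to the Day 71 sample: 71 − 43 = 28 days, range 71 − 46 = 25 to 81 − 40 = 41. The continued part of Protocol Table 1 prints ±10 days for Day 71, which would make the lower end 61 − 46 = 15.

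**Actual timing by 15 April 2020** (more than 7 days past the window; earlier doses assumed in window)
- One-dose women: window ended Day 25, so at least Day 33, or 33 − 1 = 32 days since dose 1 (planned 18 to 24).
- Two-dose woman: window ended Day 46, so at least Day 54, or 54 − 25 = 29 days since dose 2 (planned 15 to 27).
- Three-dose women: no firm minimum. The protocol says only that nobody completed *all* Day 71 assessments. It also says "The first subject was dosed with CCH on 26 December 2019", which puts that subject's Day 71 at 5 March 2020 and the end of her window (Day 81) at 15 March, before the suspension. A Day 71 sample could already have been drawn. If one had not been drawn by 15 April, the woman would be at Day 89 or later, at least 89 − 46 = 43 days after dose 3 (planned up to 41).

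The only written anchor for visits is the date of the first dose (Protocol Table 1, footnote i). The documents do not say how Day 71 is placed for a woman who resumes late.

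**Illustration on assumed values.** Suppose 100% are positive after three doses, 50% to 90% after one, and the midpoint after two, with none of the 5 resuming and all 19 sampled.
- At 50%: (14×1 + 1×0.75 + 4×0.50)/19 = 88%.
- At 90%: (14×1 + 1×0.95 + 4×0.90)/19 = 98%.
- If positivity does not depend on dose count, nothing changes.

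**The case against.** The best case against the point is that the SAP never decided to pool these women. It predates the interruption and plans for about 12 subjects, and Protocol 9.3 foresees a more detailed SAP finalised before the interim analysis. That stands: the mixing arises by omission. An update that merely follows Amendment 3 would not cure it, however, because Protocol 9.3.4 has no split either.

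The planned outputs also help. SAP 7.7.1 tabulates the number treated at each session and lists exposure and injection status. Out-of-window visits are a named deviation type (SAP 4.2), and all deviations are listed (SAP 7.2). Immunogenicity data are listed for every subject (SAP 7.7.7). For at most 7 women the dosing history can be rebuilt by hand. Even so, the summary stays mixed, and Table 12 derives Study Day from Day 1 but neither doses received nor days since the last dose.

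Mixed exposure is normal in an all-subjects safety table. The later cohort is not guaranteed to be purely three-dose either, since women who stop treatment are encouraged to keep attending (Protocol 7.1).

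Stronger readings that a reader might infer, and that the documents do not support:
- *All 7 were under-dosed or dosed off plan.* Two had the full course, and nothing says their dose intervals were wrong. The dose-count question covers at most 5 women.
- *Laboratory, vital-sign and adverse-event tables need the same split.* The documents give no mechanism that would require it.
- *The antibody results are biased in a known direction.* The documents contain no dose-response or time-course figures. They say only that the immunogenicity profile was consistent across studies.
- *These women should leave the safety data.* Keeping them is a stated and reasonable decision.

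**Conclusion.** The point holds in a narrow form and is minor. Followed as written on the Amendment 3 Safety Population, SAP 7.7.7 gives Day 71 and later antibody summaries that can combine the planned regimen with interrupted courses. Up to 5 of about 19 dosed women (26%) may contribute samples after one or two doses or a late-completed course. Another 2 (11%) had three doses, and their Day 71 samples may be late.

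These shares limit how many women are involved; they do not estimate an effect. They assume that every interrupted woman attends and that about 19 are dosed. Whether the antibody figures would move depends on a dose or time relation that is plausible but not quantified in the documents. The summaries are descriptive and no test rests on them. Efficacy is protected by the protocol's definition of the Evaluable Population, which admits only women first dosed after 18 March 2020.

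**What to change.** Change the SAP only, as part of its update to Amendment 3:
- Show binding and neutralizing antibody results by visit for subjects first dosed after 18 March 2020 as the main columns.
- Keep an all-subjects overall column.
- Present the women dosed before that date separately, preferably as a by-subject listing with doses received and days since last dose at each sample. A single combined column with a mean titre would again mix one, two and three doses.
- Leave the laboratory, vital-sign and adverse-event tables as planned.

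It would also help, though the fix does not need it, to state how visits are timed for interrupted women.

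The cost is table and listing work on dose and sample dates already collected. No protocol amendment is needed, and every woman stays in the safety data. The downside is smaller groups: about 12 in the main columns and at most 7 listed separately.

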7.8. Pharmacodynamics

Pharmacodynamic parameters, if available, will be summarized by treatment region (buttock or thigh) using the Safety Population.

7.8.1. Comparison of Baseline (Screening) MRI Tissue Morphology and Septae

A summary table and a listing will be provided based on Safety population if the data are available.

7.8.2. Comparison of Baseline (Screening) Histopathology

A summary table and a listing will be provided based on Safety population if the data are available.

8. CHANGE FROM PROTOCOL

This SAP is prepared primarily based on the study protocol; original version dated October 22, 2019 and protocol amendment 1 dated January 16, 2020.

